4.6. Demographics and Baseline Characteristics

Subject demographics and baseline characteristics will be summarized for ITT and As-Treated populations.

The continuous baseline characteristics include age (years), baseline height (cm), baseline weight (kg), baseline BMI (kg/m²), and %-predicted FEV₁ at baseline. The categorical baseline characteristics include gender, race, region, age group (<18 vs \ge 18 years), and baseline %-predicted FEV₁ group (<65% vs \ge 65%).

4.7. Medical History

The medical history will be summarized by the system organ class and preferred term. The listing of medical history will be provided as well.

4.8. Prior and Concomitant Medications and Procedures

Prior medications will be defined as those medications that were used prior to the first dose of study treatment. Concomitant medications will be defined as those medications that were used

during the study treatment period. If the start date of a medication is missing and the end date is prior to study start, the medication will be deemed prior. If the end date is after study start or is also missing, the drug will be deemed concomitant. If the end date is missing or the medication is ongoing, the medication will be considered concomitant. If the medication start date is completely missing and end date is missing or ongoing, the medication will be considered both prior and concomitant. Prior and concomitant therapies will be defined similarly.

Prior and concomitant medications will be coded by means of the World Health Organization Drug Dictionary (WHODRUG) into Anatomical-Therapeutic-Chemical classification (ATC) codes. Subject incidence of prior and concomitant medications will be tabulated by ATC level 2 and preferred term for the As-Treated population. Subjects will only count once for each ATC or preferred term in the event that they have multiple records of the same ATC or preferred term in the database.

Prior and concomitant non-drug therapies will be coded and analyzed similarly.

4.9. Study Treatment Administration and Compliance

The study treatment duration in weeks is defined as (last dose date - first dose date +1)/7 and will be summarized overall. This duration is irrespective of the dose interruptions.

The drug compliance of a specific time period is defined as 100*(number of sachets taken during the period/number of planned sachets during the period). It will be summarized for overall treatment duration. The percentages will take into account physician-prescribed reductions and interruptions.

The number and percentage of subjects having dose interruptions and dose changes will be summarized using descriptive statistics for overall treatment duration.

The above analyses will be performed for the As-Treated population.

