6. STUDY DRUG ADMINISTRATION

6.1. Investigational Product

6.1.1. Ataluren (PTC124)

Ataluren will be provided as a white to off-white powder for oral suspension. The drug has been manufactured under cGMP conditions. The formulation includes matrix and suspending agents, surfactants, and various excipients that aid in the manufacturing process. The powder for oral suspension are packaged in aluminum-foil, child-resistant sachets (packets) and supplied in dose strengths containing 125, 250, or 1000 mg of the active drug substance. For administration, the powder in the sachet may be mixed with water, milk (skim, 1% fat, 2% fat, whole milk, chocolate milk, or lactose-free milk), or in semi-solid food (yogurt, pudding, or applesauce).

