6.1.2. Drug Kits

Drug kits will be provided, each of which contains 120 sachets of one of the dose strengths (125, 250, or 1000 mg.).

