6.1.4. Study Drug Dispensing

Dosing of ataluren will be based on milligrams of drug per kilogram of patient body weight at Screening/Baseline (Visit 1) and will be adjusted to allow for dosing with the available sachet dose strengths. All subjects will receive approximately 10-, 10-, 20-mg/kg ataluren TID for ~96 weeks. The sachet dosage strengths and number of sachets to be taken per dose will be provided by the IVR/IWR system.

The clinic staff (eg, pharmacist or other qualified person) will be responsible for dispensing study drug according to the IVR/IWR system directions. Sufficient study drug will be provided for each study period at the beginning of the period.

Because of potential changes in subject body weight over time, at Week 24 (Visit 3) and Week 60 (Visit 6), the possibility of a dose adjustment will be evaluated based on the subject's body weight at that visit. Depending upon the magnitude of change in subject body weight since baseline, the number and strengths of sachets to be used by the subject may remain the same or may be adjusted.

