14.1.5 Study Drug Compliance

Evaluation of study drug compliance provides context for assessments of pharmacological activity, safety, and PK, and may offer a general indication of patient acceptance of therapy, integrating factors of tolerability, palatability, and convenience. The compliance of the patient will be verified by counting unused drug study sachets.

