2. STUDY OVERVIEW

2.1. Study Design

Study 021e is a Phase 3, international, multicenter, open-label, extension study of ataluren in patients with nmCF that have completed participation in the double-blind study PTC124-GD-021-CF (Study 021).

All eligible patients that completed participation in Study 021 will be enrolled into the study. Eligible subjects will receive oral ataluren administered 3 times per day (TID) at respective morning, midday, and evening doses of 10-, 10-, and 20-mg/kg for 96 weeks. The detailed schedule of assessments are displayed in Table 1.

Screening and baseline procedures are structured to avoid a gap in treatment between the double-blind study (PTC124-GD-021-CF) and this extension study. When possible, Screening/Baseline (Visit 1) for this extension study should occur on the same day as the End-of-Study visit for the double-blind study (PTC124-GD-021-CF). During the treatment period, study assessments will be performed at clinic visits at Week 12 and thereafter every 12 weeks until the end of the study.

Planned interim safety analyses will be conducted by an independent data monitoring committee (DMC). The first safety review will occur when ~ 100 patients have completed >=36 weeks of treatment. The second safety review will occur when ~ 100 patients have completed >=72 weeks of treatment.

The study will be terminated prematurely according to company's strategic decision on March 2, 2017. All subject who are on-going by then will be discontinued.

Table 1. Schedule of Events

| Study Period | Screening/B aseline | Treatment Period | | | | | | Post-Treatment | | |
|---|---------------------|------------------|----|----|----|----|----|----------------|-----------------------------|--------------------|
| Study Week (±7 days) | Day 1 | 12 | 24 | 36 | 48 | 60 | 72 | 84 | End of Tx/ Premature D/C 96 | 4 Weeks Post-Tx |
| Visit | 1 | 2 | 3 | 4 | 5 | 6 | 7 | 8 | 9 | 10 |
| Informed consent | X | | | | | | | | | |
| CFQ-R administration | X ^a | X | X | X | X | X | X | X | X | |
| Vital signs | Xa | X | X | X | X | X | X | X | X | X |
| Height | X ^a | X | X | X | X | X | X | X | X | X |
| Weight | X ^a | X | X | X | X | X | X | X | X | X |
| Physical examination | X ^a | | | | X | | | | X | X |
| Hematology | X ^a | X | X | X | X | X | X | X | X | X |
| Biochemistry | X ^a | X | X | X | X | X | X | X | X | X |
| Urinalysis | Xa | X | X | X | X | X | X | X | X | X |
| Renal ultrasound | Xa | | | | X | | | | X | |

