2.3.4. Other Endpoints

• Study drug extent of exposure and characterization of investigator-prescribed dosing modifications

• Study drug compliance as assessed by a subject daily diary and by quantification of used and unused study drug

• Incidence of concomitant therapies

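### SAP 4.9 counts sachets of unequal strength as equal, so the compliance percentage is not the fraction of drug taken when missed doses fall unevenly across the day

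*SAP*

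**What the plan says.** SAP 4.9 gives the formula: "The drug compliance of a specific time period is defined as 100*(number of sachets taken during the period/number of planned sachets during the period". Its only stated adjustment is: "The percentages will take into account physician-prescribed reductions and interruptions". It does not weight by strength, and it does not say how the number of sachets taken is obtained.

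The sachets are not interchangeable. Protocol 6.1.1 has the powder "supplied in dose strengths containing 125, 250, or 1000 mg of the active drug substance", and Protocol 6.1.2 describes kits, "each of which contains 120 sachets of one of the dose strengths". The day's doses are also unequal: SAP 2.1 specifies "respective morning, midday, and evening doses of 10-, 10-, and 20-mg/kg for 96 weeks". Under Protocol 6.1.4 the IVR/IWR system sets the strengths and number of sachets for each dose, with a possible change at Weeks 24 and 60. That section says "Depending upon the magnitude of change in subject body weight since baseline, the number and strengths of sachets to be used by the subject may" stay the same or be changed.

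The documents differ on the data source. SAP 2.3.4 lists "Study drug compliance as assessed by a subject daily diary and by quantification of used and unused study drug". Protocol 14.1.5 says "The compliance of the patient will be verified by counting unused drug study sachets". Protocol 8.2.16 describes an accountability log of returned unused sachets, and neither schedule of events includes a diary.

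**The concern.** A compliance percentage is normally read as the share of the prescribed drug that was taken. Here a 1000 mg sachet and a 125 mg sachet count the same, an 8-fold difference. The number of sachets in a dose depends on how its mg total splits into the three strengths, so it does not rise in step with the dose. Where the evening dose is one 1000 mg sachet and each daytime dose is two 250 mg sachets, half of the drug carries one fifth of the weight.

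The size and direction of the error then depend on body weight and on which dose is missed. Two patients who took the same fraction of their drug can get different percentages, and their ranking can reverse.

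Protocol 14.1.5 presents compliance as context for activity, safety and PK. The primary objective concerns the long-term safety of a stated mg/kg regimen. SAP 4.9 otherwise gives treatment duration regardless of interruptions, and numbers of subjects with interruptions or dose changes. SAP 6 removes the summary of plasma concentrations. The sachet percentage is therefore the main remaining summary of how much drug was taken.

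**Working it through.** The documents state no compliance figure, so there is none to reproduce. The check is direct arithmetic.

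**Inputs from the documents**
- Strengths 125, 250 and 1000 mg (Protocol 6.1.1).
- Doses 10, 10 and 20 mg/kg (SAP 2.1), so 40 mg/kg/day. Cross-check: 4 x 40 = 160 mg/kg/day, the overdose threshold in Protocol 6.1.8.
- Evening share of the day's drug: 20/40 = 50%.

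**Assumption.** The IVR/IWR table is not given. Each dose is rounded to the nearest 125 mg and made up with the fewest sachets.

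**Formulas.** Let a and b be the sachets per daytime and evening dose, and A and B the corresponding mg. If the evening dose is never taken:
- sachet compliance = 100 x 2a/(2a + b)
- mg compliance = 100 x 2A/(2A + B)

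**Worked case, 50 kg (no rounding needed).** Morning 500 mg = 2 x 250; midday 500 mg = 2 x 250; evening 1000 mg = 1 x 1000. That is 5 sachets and 2000 mg a day.
- Evening never taken: 4/5 = 80% by sachets (336/420 over 84 days); 1000/2000 = 50% by mg.
- Midday never taken: 3/5 = 60% by sachets; 1500/2000 = 75% by mg. The ranking of these two patients reverses.
- Only the evening dose taken: 1/5 = 20% by sachets; 1000/2000 = 50% by mg.

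**Other weights, evening dose never taken (selected bands)**

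| Weight (kg) | Doses (mg) | Sachets | By sachets | By mg |
|---|---|---|---|---|
| 22-28 | 250 / 250 / 500 | 1 / 1 / 2 | 50% | 50% |
| 28.5-31 | 250 / 250 / 625 | 1 / 1 / 3 | 40% | 44.4% |
| 47-53 | 500 / 500 / 1000 | 2 / 2 / 1 | 80% | 50% |
| 59.5-65.5 | 625 / 625 / 1250 | 3 / 3 / 2 | 75% | 50% |
| 72-78 | 750 / 750 / 1500 | 3 / 3 / 3 | 66.7% | 50% |
| 94-96.5 | 1000 / 1000 / 1875 | 1 / 1 / 5 | 28.6% | 51.6% |

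**Scan of 16-100 kg in 0.5 kg steps (169 weights)**
- Sachet score 28.6-80%, median 61.5%. Mg score 40-57%; its departures from 50% are dose rounding only.
- 80% at 13/169 = 8% of weights, all within 47-53 kg.
- At least 75% at about 19% of weights (47-53 and 56.5-65.5 kg).
- Sachet score more than 10 points too high at 94/169 = 56% of weights.
- Sachet score below the mg score at 24/169 = 14% of weights.

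These are shares of a grid of weights. They are not shares of the trial's patients.

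**Sensitivity to the assumption.** Rounding down moves the 80% band to 50-56 kg, and rounding up moves it to 44-50 kg; 80% stays the maximum. If 500 mg were supplied as 4 x 125 mg, the 50 kg score would be 8/9 = 89%.

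**When the error vanishes.** If each daily dose is missed at the same rate p, both measures have expectation 100 x (1 - p).

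**The case against.** The strongest reply is that the 80% figure is a worst case. It needs an assumed dispensing rule, a body weight in a narrow band, and a patient who regularly skips one particular dose. Nothing in the documents suggests that evening doses are skipped. With misses spread evenly the two measures agree on average, and at some weights the sachet count understates intake. All of this stands, and it limits the size of the point. The formula nevertheless lacks the weighting that would make it correct whatever the pattern of misses.

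The second reply is that nothing depends on compliance. The As-Treated population needs one dose, the ITT population needs one post-baseline efficacy assessment, and there is no per-protocol set. Exposure-adjusted rates in SAP 4.10.1 use days on drug. No compliance threshold is set, and SAP 4.2 calls all analyses descriptive. This stands too.

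Third, there is other information on dose. By-subject listings cover every CRF module. SAP 4.10.2 and 4.12.1 allow laboratory and vital sign findings to be described by dose as necessary. Pre-morning-dose concentrations from Weeks 24, 48, 72 and 96 are listed, and these samples follow the evening dose. The check is only partial: concentrations are listed but not summarized, and Protocol 6.2.2 asks for close adherence on the day before sampling.

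A reader might also infer two further faults that the documents do not support:
- That crediting prescribed reductions and interruptions inflates compliance. Adherence is properly judged against what was prescribed, and SAP 4.9 tabulates interruptions and dose changes separately.
- That SAP 2.3.4 requires used sachets to be returned. Used drug can be derived as dispensed minus returned. Only the diary conflicts with the protocol.

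**Conclusion.** The point holds in a limited form. As written, the SAP 4.9 percentage is a fraction of sachets, and it departs from the fraction of drug taken whenever misses are uneven across the day's doses. For a patient who never takes the evening dose, the departure ranges from 30 points too high (80% against 50%) to 23 points too low (28.6% against 51.6%). These sizes rest on the assumed rounding and fewest-sachets rule. The absence of weighting is plain from the text and needs no assumption.

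It would be tempting to conclude that the safety results could be credited to a dose that was not taken, or that the adverse event analysis is biased. The documents do not support that. Compliance enters no population, denominator or event count, and they give no evidence of systematic evening omission. What is at risk is one descriptive summary, used as context.

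The data source is a smaller matter. SAP 2.3.4 names a diary that the protocol does not collect. Because SAP 4.9 leaves sachets taken undefined, a count based on returns would treat an unreported lost sachet as taken. Protocol 8.2.15 expects some losses.

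**What to change.** In SAP 4.9, define compliance as

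100 x sum(sachets taken x strength in mg) / sum(sachets planned x strength in mg)

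Keep the adjustment for prescribed reductions and interruptions. State that sachets taken = dispensed minus returned minus reported losses, counted separately by strength. At 50 kg with no evening dose this gives 1000/2000 = 50%.

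In SAP 2.3.4, remove the diary as a source, or identify where diary data are collected, so that it agrees with Protocol 8.2.16 and 14.1.5.

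A summary of mean mg/kg/day received would be a useful optional addition, since weight is measured at every visit. It is not needed to correct the formula.

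The cost is SAP wording and slightly more programming. Kits hold a single strength, so counts by strength should be recoverable from dispensing and accountability records. SAP 1 allows refinement by amendment before database lock. Reported compliance may look somewhat less favourable.

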4.10. Primary Analyses

All primary analyses will be performed for the As-Treated population.

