4.2. Inclusion Criteria

Patients must meet all of the following conditions to be eligible for enrollment into the study:

- 1. Completion of study treatment (placebo or active) in the previous Phase 3, double-blind study protocol (Protocol PTC124-GD-021-CF).
- 2. Evidence of signed and dated informed consent/assent document(s) indicating that the patient (and/or his parent/legal guardian) has been informed of all pertinent aspects of the trial. *Note: If the study candidate is considered a child under local regulation, a parent or legal guardian must provide written consent prior to initiation of study screening procedures and the study candidate may be required to provide written assent. The rules of the responsible Institutional Review Board/Independent Ethic Committee (IRB/IEC) regarding whether one or both parents must provide consent and the appropriate ages for obtaining consent and assent from the patient should be followed.*
- 3. In patients who are sexually active, willingness to abstain from sexual intercourse or employ a barrier or medical method of contraception during the study drug administration and 4-week follow-up period.
- 4. Willingness and ability to comply with scheduled visits, ataluren administration plan, study procedures, laboratory tests, and study restrictions.

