In addition, in clinical trials in nmDMD the adverse-event profile of ataluren was comparable to that of placebo. In the double-blind Phase 2b study of nmDMD, six patients – all receiving corticosteroids - had hypertension (or increased blood pressure) reported as adverse events (0 for ataluren 20-, 20-, 40-mg/kg, 5 for ataluren 10-, 10-, 20-mg/kg, and 1 for placebo), although similar events were not seen in the nmCF studies. Mean total cholesterol and triglycerides were in the upper range of normal at baseline and increased, reaching borderline high or high values. The values tended to stabilize early in the study and did not increase further with continued treatment. Small increases in mean serum creatinine, BUN, and cystatin C were observed. Similarly, the values tended to stabilize early in the study and did not increase further with continued treatment.

Collectively, the safety data from clinical trials demonstrate that ataluren has a favorable safety profile for the treatment of patients with nmCF.

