4.10.2. Clinical Laboratory Evaluations

Hematology laboratory assessments will include white blood cell count with differential, hemoglobin, hematocrit, mean corpuscular volume, mean corpuscular hemoglobin, mean corpuscular hemoglobin concentration, total red cell count with morphology, and platelet count. These parameters will be measured at all study visits.

Biochemistry laboratory assessments will include sodium, potassium, chloride, bicarbonate, blood urea nitrogen, creatinine, magnesium, calcium, phosphorus, uric acid, glucose, total protein, albumin, globulin, albumin:globulin ratio, bilirubin (total, direct and indirect), creatine kinase (CK), lactate dehydrogenase (LDH), alanine aminotransferase (ALT), aspartate aminotransferase (AST), gamma glutamyl transferase (GGT), alkaline phosphatase, total cholesterol, high-density lipoprotein (HDL), low-density lipoprotein (LDL), triglycerides, and cystatin C. These parameters will be measured at all study visits. Ideally, subjects should have fasted for at least 8 hours prior to blood collection.

Urinalysis assessments will include pH, specific gravity, glucose, ketones, blood, protein, creatinine, urobilinogen, bilirubin, nitrite, and leukocyte esterase. These parameters will be measured at all study visits.

Hematology, serum biochemistry, and urinalysis data and their changes from baseline (only for continuous laboratory parameters) will be summarized by visit. Maximal and minimal change from baseline in each parameter will also be summarized.

Shift tables for hematology, serum biochemistry, and urinalysis will also be presented showing change in CTCAE severity grade from baseline to each visit. For parameters for which a CTCAE scale does not exist, shift tables will be presented showing change in results from baseline (normal, low, and high [or abnormal]) to each visit (normal, low, and high [or abnormal]).

Frequency tables will be presented for safety monitoring parameters to show the number and percentages of subjects by severity grade categories defined in Table 2. If a CTCAE grade does not exist, abnormal results will be summarized by protocol-defined thresholds as noted in Table 2. Subjects will be characterized only once for a given assay, based on their worst severity grade observed during the time period of interest.

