4.11.1. Change from Baseline in %-predicted FEV₁

The descriptive statistics of %-predicted FEV₁, absolute, and relative change in %-predicted FEV₁ will be summarized for each visit overall and by preceding treatment group in PTC124-GD-021-CF (study 021). The highest FEV₁ assessment at each visit will be included into the analyses.

4.11.2. **Pulmonary Exacerbations**

The descriptive statistics of the 48-week pulmonary exacerbation rates based on different definitions in Section 5.6 will be reported. The number of subjects with $0, \ge 1, \ge 2$, and ≥ 3 pulmonary exacerbations based on different definitions will also be tabulated as well.

Descriptive statistics of the overall duration of pulmonary exacerbations will be reported.

The above analyses will be performed by preceding treatment group in study 021 and overall.

4.11.3. **FVC**

The absolute change in FVC will be analyzed using descriptive statistics for each visit overall and by preceding treatment group in study 021.

^b Patients with a diagnosis of Gilbert's syndrome need not confirm the laboratory parameter and/or stop study drug unless the total bilirubin value exceeds 3.0 x ULN.

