5.1. Baseline

In general, Baseline is defined as the last non-missing valid assessment prior to or on the date of the first dose. The assessment at week 48 in study 021 will be used as the baseline if corresponding baseline in study 021e is missing.

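### Exposure, adverse event and laboratory tables pool patients starting ataluren with patients continuing it, although efficacy is split by preceding Study 021 treatment

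*SAP*

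**What the plan says.** Entry requires "Completion of study treatment (placebo or active) in the previous Phase 3, double-blind study protocol" (Protocol 4.2), so both former placebo and former ataluren patients enter. SAP 3.1 places everyone with at least one ataluren dose in a single As-Treated set.

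- **Exposure (SAP 4.9):** "The study treatment duration in weeks is defined as (last dose date - first dose date +1)/7 and will be summarized overall".
- **Primary safety analyses (SAP 4.10):** "All primary analyses will be performed for the As-Treated population". In 4.10.1 the adverse event tables are laid out by organ class, preferred term, grade and relationship, and patient-years are summed over all patients.
- **Laboratory data (SAP 4.10.2):** "Hematology, serum biochemistry, and urinalysis data and their changes from baseline (only for continuous laboratory parameters) will be summarized by visit". Shift tables and threshold frequencies follow. None of these names preceding Study 021 treatment.
- **Efficacy (SAP 4.11.1):** FEV₁ results "will be summarized for each visit overall and by preceding treatment group in PTC124-GD-021-CF (study 021"). SAP 4.11.2 and 4.11.3 apply the same split to exacerbations and FVC.
- **Baseline (SAP 5.1):** the last valid value on or before the first dose. In addition, "The assessment at week 48 in study 021 will be used as the baseline if corresponding baseline in study 021e is missing".
- **Rollover (SAP 2.1):** "Screening and baseline procedures are structured to avoid a gap in treatment between the double-blind study (PTC124-GD-021-CF) and this extension study".

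**The concern.** The primary objective is long-term safety, and the primary endpoint in SAP 2.3.1 includes the timing of adverse events and laboratory abnormalities. In a pooled table, an event at Week 12 of 021e counts the same whether the patient has had 12 weeks of ataluren or about 60. A reader cannot tell whether it belongs to first or to continued exposure, and the 4.9 table does not show which patients bring 48 weeks of earlier treatment.

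The baseline rule adds a second problem. A laboratory shift that arose during Study 021 is already inside the baseline of a former ataluren patient who rolled over without a gap. It cannot appear as change or as a shift for that patient, and it dilutes whatever the former placebo patients show. The programme gives some reason to expect such a pattern. In the paragraph on the nmDMD trials, Protocol 15.3 reports "Small increases in mean serum creatinine, BUN, and cystatin C were observed" and says the values tended to stabilise early.

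**Working it through.** The plan has no figure of its own to reproduce: the sample size rests on no hypothesis (SAP 2.4) and all analyses are descriptive (SAP 4.2). The check is a comparison of sections followed by conditional arithmetic.

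**Grouping stated in each section**

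| Analysis | SAP section | Split by preceding 021 treatment |
|---|---|---|
| Exposure, compliance, dose changes | 4.9 | No; overall |
| TEAEs, SAEs, exposure-adjusted rates | 4.10.1 | None stated |
| Laboratory change, shift, thresholds | 4.10.2 | None stated |
| FEV₁, exacerbations, FVC | 4.11.1–4.11.3 | Yes, plus overall |

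SAP 6, which lists changes from the protocol, gives no reason for the difference.

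**Cumulative exposure.** Study 021 has 48 planned weeks (Protocol 14.2.2) and 021e up to 96 (Protocol 6.2.1). At the planned maximum a former placebo patient has 96 weeks of ataluren and a former ataluren patient 96 + 48 = 144, a ratio of 144/96 = 1.5. If the first dose in 4.9 means the first 021e dose, both are tabulated as 96.

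SAP 2.1 records early termination, with the date 2 March 2017. First dosing in Study 021 was on 15 August 2014 (Protocol 1). Adding 48 weeks gives 17 July 2015, which is 594 days, or 594/7 ≈ 85 weeks, before that date. If dosing stopped then (the SAP wording leaves open whether this is the date of the decision or of the stop), no patient reaches 96 weeks within 021e. The longest-treated former ataluren patient could have about 85 + 48 = 133 weeks.

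**Dilution.** Let q be the former placebo share of patients (of patient-years, for exposure-adjusted rates). Let r be the rate or mean shift in former ataluren patients relative to former placebo patients. Then pooled value / former placebo value = q + (1 − q)r. Neither q nor r is in the documents, so both are assumed:

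| q | r = 0 | r = 0.5 | r = 1 |
|---|---|---|---|
| 1/3 | 0.33 | 0.67 | 1 |
| 1/2 | 0.50 | 0.75 | 1 |
| 2/3 | 0.67 | 0.83 | 1 |

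As a hypothetical example, an early event at 6% in new starters and 2% in continuing patients pools to 6q + 2(1 − q) = 3.3%, 4.0% and 4.7% for the three values of q.

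Pooling also hides the opposite case, where risk rises with cumulative exposure. Pooled value / former ataluren value = [q + (1 − q)r]/r. At r = 2 this is 0.83, 0.75 and 0.67 for q = 1/3, 1/2 and 2/3.

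**Precision of split columns.** With zero events in n patients, the one-sided 95% upper bound is 1 − 0.05^(1/n).

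| Total assumed in 021e | Pooled bound | Former placebo column, q = 1/3, 1/2, 2/3 |
|---|---|---|
| 200 (Protocol 5.1) | 1.49% | n = 67, 100, 133: 4.37%, 2.95%, 2.23% |
| 279 (upper bound, SAP 2.4) | 1.07% | n = 93, 140, 186: 3.17%, 2.12%, 1.60% |

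**The case against.** The best opposing argument is that SAP 4.10 names an analysis population and not a column layout. SAP 4.11 also opens with one population and then splits within it. The phrases about an ataluren group in 4.10.1 and a treatment group in 4.12.4 could hint at more columns. They define none, however, and 4.9 says overall outright. The accurate reading is that no split is stated for the safety tables, and that is enough for the point.

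Several mitigations are real:

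- Laboratory values, as well as changes, are summarised by visit.
- Shift tables show an abnormal baseline grade even when nothing shifts.
- The Table 2 threshold frequencies do not depend on baseline.
- Renal events are listed by nephrotoxic drug use.
- Patient numbers carry over from Study 021, so listings can be linked to the earlier arm.
- SAP 4.10.2 allows laboratory abnormalities to be described by duration of exposure. That is only as necessary, covers laboratory data alone and does not name prior treatment.

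None of these commits the plan to tables separating starters from continuers.

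Study 021 itself compares the first 48 weeks with concurrent placebo, which is stronger evidence on early effects than an uncontrolled former placebo column. This stands, but it does not make the pooled 021e tables interpretable. Protocol 11.4.5 has no such split either, so the SAP has dropped nothing that was promised.

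The consequence may also be small. In CF Study 009 (Protocol 14.2.4) creatinine did not differ meaningfully between arms at Week 48, and all 7 renal serious events were associated with nephrotoxic antibiotics. Renal events may therefore depend little on time since first dose. Some former ataluren patients may also have an off-drug baseline, because Protocol 7.1.2 and Table 3 foresee gaps.

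**Conclusion.** The point holds. The plan states no split by preceding treatment for its primary safety analyses while applying one to its secondary efficacy analyses. Its baseline rule gives the two groups different kinds of baseline whenever rollover is gap-free. No error rate is affected, because everything is descriptive; what suffers is the reading of the safety profile, above all its timing.

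The size depends on unknown inputs. For an assumed former placebo share of 1/3 to 2/3, the pooled value is 33% to 67% of the former placebo value if the effect is confined to starters, 67% to 83% if continuing patients have half of it, and undiluted if the groups are alike. The textual finding is firm; the consequence is plausible but unproven, and without the split the reader cannot tell which case applies. The change should be made, but the analysis is not invalid without it.

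**What to change.** Present the SAP 4.9 exposure tables and the 4.10.1 and 4.10.2 tables (TEAEs, SAEs, exposure-adjusted rates, laboratory change and shift) by preceding Study 021 treatment group plus overall, descriptively, as 4.11 does. State in 4.9 whether duration is counted within 021e only or cumulatively. Define the treatment group named in 4.12.4 for the renal ultrasound tables.

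As a secondary addition for former ataluren patients, show laboratory change from the Study 021 pre-treatment baseline and exposure accumulated from the first ataluren dose.

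The main change uses a variable already in the analysis. Its cost is precision within columns: with about 200 patients, zero events in the former placebo column would exclude only rates above 4.4% to 2.2%, against 1.5% pooled, and the overall column remains. The secondary addition needs linkage to Study 021 baselines and dosing dates, beyond the Week 48 values the SAP already draws on, and can be left to an integrated safety report if that is impractical.
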